According to another study, male patients had greater rates of urolithiasis than female patients. Similar results were obtained by other researchers [18] in their investigation, with male to female ratios of 3.3:1, 1.35:1, and 1.8:1, respectively. The explanation for the increased frequency in male patients may be because androgens, which are more prevalent in men than in women, encourage the production of stones. Estrogens, on the other hand, repress stone formation(17).

Risk Factors

The development of ureteric calculi is influenced by an unknown number of predisposing variables. Dietary practices, hydration levels, and coexisting conditions such as obesity and diabetes mellitus are significant contributors to its etiopathogenesis. Though several hypotheses have been put up to explain the genesis and progression of urologic calculi, none have been able to provide a comprehensive response to the questions surrounding the formation of stones(18).

Urolithiasis development is aided by bacteria. Ammonium urate, magnesium ammonium phosphate, and carbonate apatite are the constituents of infection stones that are formed by urease-producing bacteria infections that persist. However, non-infection stones like calcium phosphate and oxalate may serve as a breeding ground for bacteria. Layers of urine bacteria are incorporated into the growth of urinary stones. According to our univariate analysis, patients with urosepsis were more likely than those in the non-urosepsis group to have infection stones, as well as positive urine and stone cultures. These findings suggest that the urosepsis group in this study had a persistent UTI prior to the bacteria forming ureteral stones(19).

Most Common Presenting Complaint

Most common symptom with which patients of ureteric stone present is colicky pain in lumbar region(20). In addition to incidental findings, urolithiasis can manifest as fever, nausea, vomiting, and loin discomfort. If a patient exhibits symptoms that point to an infection or a single kidney, they ought to be investigated immediately. Urinary tract symptoms (LUTS) are the most common way that bladder stones manifest, although haematuria and suprapubic pain can also be present(4).

Adults frequently complain of macroscopic hematuria, poorly localized pain, and irritability, while younger children are more prone to present with nonspecific symptoms like vomiting and irritation(21).

Treatment Options.

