All things considered, the thorough examination of the exclusions, withdrawals, and reported adverse effects in the pooled analysis sheds light on the difficulties and conclusions that have been found in a number of research. It emphasizes how crucial it is to closely monitor participant outcomes and unfavorable occurrences in clinical research in order to guarantee the efficacy and safety of the medicines being studied(30).

The treatment for distal ureteral stones with size less than 10 mm with tamsulosin and silodosin has resulted in a high output rates of 57-64% and 80 - 84%, respectively, according to randomized controlled studies. Nonetheless, compared to other trials, the tamsulosin success rate in those investigations is somewhat lower (31). However, tamsulosin demonstrated an 86% success rate in a randomized controlled study with almost 3000 patients(32). Tamsulosin has a 67–90.7% success rate in treating distal ureteral stones, according to Tao

et al.'s meta-analysis.20 The current study's tamsulosin success rates align with some studies (33).

Similar to the current investigation, the comparable rates in the Imperatore et al. study were 82% and 88%, and in the Arda et al. study they were 72.4% and 78.6%. These investigations also revealed no discernible difference between tamsulosin and silodosin. However, only young/middle-aged men were included in this study, whereas both of other investigations included both men and women. This sums up the main distinction between prior studies and the present investigation (34).

Tamsulosin is used commonly in our population for MET however Silodosin, a newer drug, is not used frequently for this purpose and is still under research. Also, comparison of Silodosin and Tamsulosin has not been explored in our population earlier.

Rationale

The purpose of this study is to examine and compare the effectiveness of silodosin and tamsulosin in medical expulsive therapy (MET) in terms of the rate at which stones are expelled from the body, as well as the adverse effect profiles in our patient group.

OBJECTIVES:

To evaluate and compare the efficacy and safety of medical expulsive therapy containing tamsulosin and silodosin, specifically.

To compare the side effect profile of tamsulosin and silodosin when given for medical expulsive therapy.

HYPOTHESIS:

Null Hypothesis:

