It is hypothesized that efficacy and safety of medical expulsive therapy, containing tamsulosin and silodosin, is almost the same and silodosin can be used with the same efficacy for the treatment of lower urinary tract calculi.

Alternative Hypothesis:

Silodosin is better than Tamsulosin in efficacy and safety.

OPERATIONAL DEFINITIONS:

STONE CLEARANCE:

Stone clearance will be defined as no evidence of stone on follow up X-ray KUB imaging at 4 weeks .

ANCILLARY PROCEDURES:

Additional urological procedures needed to remove the same stone for which medical expulsive therapy was given if it fails to remove the stone completely.

SIDE EFFECTS:

Any undesirable effect noticed after prescription of the drug including but not limited to abnormal ejaculation, headache, orthostatic hypotension, backache and gastritis etc.

MATERIALS AND METHODS:

STUDY DESIGN:

Prospective randomized control trial.

STUDY SETTING:

Outpatient department of Sir Ganga Ram hospital, Lahore.

DURATION OF STUDY:

18 months.

DURATION OF TREATMENT:

Four weeks.

SAMPLE SIZE:

Using the open-epic software, the sample size was estimated. The minimum sample size that we require is 208 patients with ureteric stone who fulfil the inclusion criterion with 104 in one group receiving tamsulosin and 104 in silodosin group (1:1 ratio) with an inflation of 10 percent for estimated loss to follow up, with an anticipated expulsion rate ranging from 58-64 percent in tamsulosin group and 78-83 percent in silodosin group with a risk difference of 19 to achieve a power of 80 percent and a level of significance of 5 percent.

SAMPLING TECHNIQUE:

Patients visiting the outpatient department of Sir Ganga Ram hospital will be selected by simple random sampling, fulfilling the inclusion criteria.

SAMPLE SELECTION:

Adult male and female patients fulfilling the inclusion criteria will be assigned into two groups by random allotment, 1^{st} group will be given Tamsulosin and 2^{nd} group will be given Silodosin for four weeks.

INCLUSION CRITERIA:

Following factors make up the inclusion criteria for this study.

- Patients between ages 18 years 55 years.
- Solitary unilateral ureteral stone
- Stone sizes less than 10 mm measured on non-contrast computed tomography of kidney, ureter and bladder.
- Stones being treated primarily with medical expulsive therapy
- Radio opaque Stone

EXCLUSION CRITERIA:

The presence of following factors will exclude the patients from our study:

- Pregnancy
- Untreated UTI

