- Bleeding disorders
- Obstruction distal to stone
- Serum Creatinine > 1.3 mg/dl in males and > 1.2 mg/dl in females.
- Congenital renal anomaly/ skeletal malformation
- Previous treatment for the same stone (PCNL/ URS / push back)
- Solitary Kidney
- Prior JJ stent insertion
- Bilateral ureteral stone

DATA COLLECTION AND PROCEDURE:

The protocol will be submitted to Ethical review committee for review and only once the permission is granted, the study will be started. Patients will undergo standard procedure like detailed history taking, examination and routine investigations. Once decided that the patient will undergo MET, the patient will be explained in detail about medications, their potential side effects, follow up and the potential indications for early follow up. Our study will not change any standard process in place except the randomization between Tamsulosin and Silodosin. The data will be kept confidential as a top priority. Only principal investigator and co-principal investigator will have access to the data.

All patients as per inclusion and exclusion criteria as described above will be included in the study. The CT scan (non contrast computed tomography) will be done on (machine parameters at Ganga ram). Only patients with radioopaque stones will be included. Patients falling into the inclusion criteria will be explained about the study and once they agree to participate in study, randomization will be done. Demographic data including patients' age and comorbid, stone-related data including size, location, laterality and number of stones and duration of symptoms will be recorded. The patient will be given either Capsule Tamsulosin 0.4 mg once daily at night or Tablet Silodosin 8 mg once daily at night based on the group assigned. The patient will also be explained about the reasons for follow up earlier than four weeks including fever, persistent pain or gross hematuria. The patients will be called for follow up at 4 weeks with an X-ray KUB without bowel preparation. We will note if the stone has passed or not.

ETHICAL CONSIDERATION:

The funds for supporting this research will be provided by department of pharmacology and therapeutic FJMU, Lahore. Informed consent will be taken from patients prior to research.

DATA ANALYSIS PROCEDURE:

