	Mid	08(17.4%)	38(82.6%)	0.001
	Distal	41(51.9%)	38(48.1%)	
Water intake	Less than 1 litre	59(54.6%)	49(45.4%)	
	More than 1 litre	18(25.4%)	53(74.6%)	0.001
Analgesic requirement	Yes	26(61.9%)	16(38.1%)	0.005
	No	51(37.2%)	86(62.8%)	
Time for removal	Less than 14 days	6(10.3%)	52(89.7%)	
	14-21	14(27.5%)	37(72.5%)	0.001
	22-28	57(81.4%)	13(18.6%)	

presented as frequency and percentage with association

The table compares several factors along with the corresponding p-values to assess statistical significance between two drugs tamsulosin and silodosin.

First, based on Body Mass Index (BMI), 43.4% of those with a normal BMI were prescribed Tamsulosin, while 56.6% were recommended Silodosin. On the other hand, among those who were obese, 38.5% were given Tamsulosin and 61.5% were given Silodosin; p-value came out to be 0.730, which meant that there was no statistically significant variation in the medication preferences according to BMI.

15.2% of patients who had pain for more than a week prior to CT scan, received Tamsulosin while 84.8% received silodosin.

51.9% of the patients with proximal ureteric stone were given Tamsulosin and 48.1% received Silodosin.

82.6 percent of patients with mid-ureteric stone problems received Silodosin, while 17.4% received Tamsulosin.

51.9% of patients with distal ureteric stones received Tamsulosin and 48.1% on Silodosin.

Only 38.1% of patients on Silodosin required analgesics, whereas 61.9% of patients on Tamsulosin used analgesics.

89.7% of patients on silodosin had their stone removed in less than 14 days, while only 10.3% of the patients on Tamsulosin had their stone removed in aforementioned duration.

72.5% of patients on Silodosin had their stone removed in 14-21 days, while only 27.5% of the patients on Tamsulosin had their stone removed in same duration.

Moreover, 81.4% on Tamsulosin had their stone removed in 22-28 days and 18.6% patients on Silodosin had it removed in same duration.

		Tamsulosin	Silodosin	p- value
Side	None	61 (40.1%)	91(59.9%)	
effect	Othostatic	09 (60.0%)	06(40.0%)	
	hypotension			0.3.15
	Abnormal	2(66.7%)	1(33.3%)	
	ejaculation			
	Headache	5(55.6%)	4 (44.4%)	

Table 2 Association between Tamsulosin and Silodosin with side effects

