The side effects that patients using silodosin and tamsulosin experienced are analyzed in the table, and the p-value denotes the statistical significance of these data. Patients on Silodosin, with no side effects were 59.9% while 40.1% on Tamsulosin did not report any side effects. This implies that, in comparison to Tamsulosin, Silodosin may have a marginally higher correlation with patients reporting no adverse effects.

Examining particular side effects reveals various themes. Nine patients on tamsulosin (60.0%) and six patients on silodosin (40.0%) developed orthostatic hypotension, a condition marked by a considerable drop in blood pressure upon

standing. It suggested that Tamsulosin users are more likely to have orthostatic hypotension than Silodosin users.

Only a very tiny percentage of patients reported abnormal ejaculation; 2 individuals on tamsulosin (66.7%) and 1 patient on silodosin (33.3%). Again, this points to an increased chance of this specific adverse effect in Tamsulosin users.

[figure not shown]
Another side effect that was identified involved headaches, which were seen by 4 individuals on silodosin (44.4%) and 5 patients on tamsulosin (55.6%). Headaches were marginally more common among Tamsulosin users compared to Silodosin users, similar to orthostatic hypotension.

None of the detected differences in side effect distribution between Tamsulosin and Silodosin is statistically significant, according to the p-value of 0.315. This implies that even if there are discernible variations in the frequency of particular adverse effects between the two drugs, these variations might just be the result of random variation rather than an actual distinction in the side effect profiles of tamsulosin and silodosin.

In conclusion, the analysis of side effects reveals that patients taking silodosin have a tendency to report no side effects more often than individuals taking tamsulosin. On the other hand, it seems that tamsulosin users are more likely to experience certain adverse effects, like headache, orthostatic hypotension, and abnormal ejaculation. Even with these findings, the absence of statistical significance suggests that more investigation using larger sample sizes would be necessary to conclusively identify any significant variations in the side effect profiles of Tamsulosin and Silodosin.

Figure 2

Bar Chart showing comparison of stone expulsion rate in Tamsulosin and

Silodosin groups

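### The side-effect definition has no new-or-worse rule, so stone pain can count against the slower-clearing arm, and the printed side-effect table does not follow the definition

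*Combined protocol and SAP*

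**What the plan says.** The Side Effects entry under Operational Definitions reads: "Any undesirable effect noticed after prescription of the drug including but not limited to abnormal ejaculation, headache, orthostatic hypotension, backache and gastritis etc". It sets no baseline comparison, no requirement that the effect be new or worse, and no attribution rule.

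The Literature Review, under Most Common Presenting Complaint, states: "Most common symptom with which patients of ureteric stone present is colicky pain in lumbar region". It also lists nausea and vomiting among the ways stones present. Data Collection and Procedure tells patients the "reasons for follow up earlier than four weeks including fever, persistent pain or gross hematuria", so pain from the stone is expected during treatment. The same section provides for a detailed history before treatment. Of the symptoms, however, it names only their duration as an item to be recorded.

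Safety is a stated aim. The second objective is "To compare the side effect profile of tamsulosin and silodosin when given for medical expulsive therapy", and the alternative hypothesis claims better safety for silodosin.

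In Results, the table headed "Table 2 Association between Tamsulosin and Silodosin with side effects" has four rows: none, orthostatic hypotension, abnormal ejaculation and headache. Analgesic requirement and time to stone removal are in the preceding table of study variables.

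**The concern.** Backache is named as a side effect, and lumbar pain is the leading symptom of the disease under treatment. Read literally, the rule lets pain from a stone that has not yet passed count as an undesirable effect of the drug. If one arm keeps its stones longer, its patients have more time in which to report such pain. The safety endpoint would then partly measure efficacy.

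The table raises a second problem. Two of the five effects that the definition names, backache and gastritis, have no row, and there is no row for anything else. The reader cannot tell whether these effects did not occur, were not recorded, or were placed under None. Results and Discussion nevertheless compare the arms on the None row, and the Conclusion calls silodosin safer.

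**Working it through.** **1. Does the table account for everyone?** Counts from the side-effect table:
- Tamsulosin: 61 + 9 + 2 + 5 = 77.
- Silodosin: 91 + 6 + 1 + 4 = 102.
- Total: 77 + 102 = 179, the number given in Results.

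The four rows exhaust both arms, so no patient is left for backache, gastritis or other.

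**2. The plan's own figure.** Pearson chi-square on the 4×2 table, without correction, gives 3.543 on 3 df, p = 0.315. This reproduces the reported p-value.

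**3. What makes up the printed excess?** The table's percentages are shares of each row (for example "Nine patients on tamsulosin (60.0%) and six patients on silodosin (40.0%) developed orthostatic hypotension"). Using arm totals as denominators instead:

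| Event | Tamsulosin | Silodosin |
|---|---|---|
| Orthostatic hypotension | 9/77 = 11.7% | 6/102 = 5.9% |
| Abnormal ejaculation | 2/77 = 2.6% | 1/102 = 1.0% |
| Headache | 5/77 = 6.5% | 4/102 = 3.9% |
| Any tabulated effect | 16/77 = 20.8% | 11/102 = 10.8% |

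The 10.0-point gap consists entirely of these three types. None of it is tabulated as back pain.

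**4. Did time with a stone differ between arms?** The removal-time rows (under 14, 14–21 and 22–28 days) are 6, 14, 57 for tamsulosin and 52, 37, 13 for silodosin. Removal at days 22–28 is 57/77 = 74% v 13/102 = 13%. With assumed midpoints of 7, 17.5 and 25 days:
- Tamsulosin: (6×7 + 14×17.5 + 57×25)/77 = 22.2 days.
- Silodosin: (52×7 + 37×17.5 + 13×25)/102 = 13.1 days.

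The condition for the bias is therefore present.

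**5. How large could the bias be?** The documents do not say how often stone pain would be coded as a side effect, so this step is an illustration. Assume the same drug-related rate d = 10.8% in both arms, and a constant rate h per day, while the stone is present, of pain being counted. For an arm with counts nₖ at midpoints mₖ and total N:

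P(any side effect) = 1 − (1 − d) × Σ nₖ·exp(−h·mₖ) / N.

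| h per day | Tamsulosin | Silodosin | Spurious excess (points) |
|---|---|---|---|
| 0.0025 | 15.6% | 13.7% | 2.0 |
| 0.005 | 20.2% | 16.4% | 3.7 |
| 0.01 | 28.5% | 21.6% | 6.9 |
| 0.02 | 42.5% | 30.8% | 11.7 |
| 0.07 | 79.5% | 60.7% | 18.8 |
| 0.3 | 99.0% | 94.3% | 4.8 |

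The excess rises, peaks near 19 points, then falls because almost everyone in both arms is counted. A higher true drug-related rate on silodosin cancels it: about 15% at h = 0.005, 19% at 0.01 and 26% at 0.02.

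**6. Who is in the None row?** Analgesics were required by 26 tamsulosin and 16 silodosin patients. Only 16 and 11 patients have any tabulated effect. Even if every one of those also needed analgesics, 26 − 16 = 10 tamsulosin and 16 − 11 = 5 silodosin analgesic users must be in None. These are minimums.

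**7. What if that pain were counted?** The Discussion attributes the analgesic need to ureteric pain. Assume the need arose after prescription and counts under the definition. Any side effect then becomes:
- Full overlap with tabulated effects: 26/77 = 33.8% v 16/102 = 15.7%, gap 18 points.
- No overlap: (26 + 16)/77 = 54.5% v (16 + 11)/102 = 26.5%, gap 28 points.
- Mixed extremes: 33.8% − 26.5% = 7 points, and 54.5% − 15.7% = 39 points.

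The safety result therefore depends heavily on a coding choice that the plan does not make.

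**The case against.** Four objections deserve weight.

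- **An effect noticed after prescription naturally means a newly noticed one.** The colic that led to diagnosis was noticed earlier, a history is taken before treatment, persistent pain is handled as a reason for early return, and analgesic need is tabulated separately. This is a fair reading, and the printed table is consistent with it. But the definition does not say so, it names backache, and no baseline symptom list is specified that would separate new pain from continuing pain.
- **The printed data show no contamination.** This stands. A reader might infer that retained stones explain the 10-point gap. The rows exclude that as far as they go, because the gap is hypotension, ejaculation and headache.
- **The bias is neither certain nor of known size.** This also stands. A reader might infer that the slower arm must look less safe whatever its drug does. Step 5 shows that a sufficiently higher drug-related rate in the other arm cancels or reverses the excess. A reader might also multiply the day 22–28 proportions by an assumed share with pain: (0.740 − 0.127) × 0.2 = 12 points, or × 0.5 = 31 points. That gives patients who expelled earlier no pain at all, although every patient had a stone at the first dose. It also ignores patients already counted for another effect.
- **Moving all back pain and nausea out of the safety table would hide real drug effects.** This is correct. The Literature Review lists nausea among adverse effects in treatment arms, and the Discussion cites backache with silodosin and nausea with both drugs. The fix has to keep new events of these kinds in the safety table.

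In addition, Results itself reports non-significance and asks for larger samples, which tempers its reading of the table. The Conclusion does not carry that caution over.

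**Conclusion.** The point holds in two limited parts. First, the definition leaves the safety comparison open to stone symptoms, with a likely direction against the slower-clearing arm. The size cannot be determined from the documents, and the figures in step 5 rest on assumed midpoints, an assumed common drug-related rate and an assumed coding rate. The printed 20.8% v 10.8% is not evidence that the bias operated.

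Second, the table does not follow the definition. The absence of rows for backache, gastritis and other is plain arithmetic, as is the presence of at least 10 and 5 analgesic users in None. That None therefore cannot mean free of undesirable effects further assumes that the analgesic need arose during treatment, which is how the Discussion presents it. Whether backache and gastritis were absent, unrecorded or dropped cannot be told.

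Because side effects are an objective and the Conclusion rests a safety claim on them, this should be corrected.

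**What to change.** **Definition.** Define a side effect as an undesirable effect that is new, or worse than at the pre-treatment history, after the first dose. Record the listed terms, together with the stone-type symptoms, at that existing history.

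**Reporting.** Keep new or worsened back pain, nausea and vomiting in the safety table, on separate rows. Give the any-side-effect rate with and without these stone-type symptoms. Tabulate every predefined term plus other, by arm, with arm totals as denominators.

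**Data already collected.** Where baseline symptoms cannot be recovered, do not reconstruct them. Relabel None as none of these three, say whether backache and gastritis were absent or not recorded, and limit the safety conclusion accordingly.

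**Cost.** A short checklist at an existing visit and one re-tabulation. The small downside is that a drug effect which merely continues a baseline symptom unchanged is not counted. The change concerns measurement and reporting only.

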Results: Our results showed that Silodosin turned out to be better in expulsing stone as well as in producing lesser side effects and hence better safety profile than Tamsulosin. Silodosin showed greater stone expulsion rate with about 55 patients expulsing stone in less than 14 days in comparison to just about 5 patients on Tamsulosin. Similarly, patients on Silodosin, showed lesser side effects as compared to Tamsulosin. Nine patients on tamsulosin (60.0%) and six patients on silodosin (40.0%) developed orthostatic hypotension. Only a very tiny percentage of patients reported abnormal ejaculation; two individuals on tamsulosin (66.7%) and one patient on silodosin (33.3%). Another side effect that was identified involved headaches, seen by four patients on silodosin (44.4%) and five patients on tamsulosin (55.6%).

INTRODUCTION

Stone disease is one of the most frequent presentations in the field of urology. A large number of these patients arrive with ureteric stones(1). Globally, occurrence of stone formation is 10-12% for men and 6-8% for women. Its prevalence in Pakistan is approximately 16%. The disease's burden has increased in all age categories and both genders over the past 20 years(2). The incidence of urolithiasis in different age groups is 12.2% in the persons 20-29 year old, 29.6% in those who are 30-39-year-old, and 31.5% in 40–49-year-old patients(3).

Medical management ae well as surgical removal are various options available for treating ureteric stones as per American Urology Association (AUA) and European Association of Urology (EAU) guidelines. However, due to risks of surgical approaches there is always an attempt for treatment by using medical expulsive treatment (MET) for ureteric stones first keeping in view different parameters. According to European Association of Urology Guidelines (EAU), the ureteric stones less than 10 mm can be treated with MET(4). Medical expulsive therapy (MET) is a well-established treatment option for distal ureteric stones, despite a sharp increase in minimally invasive techniques(5). Stones smaller than 5 mm have passage rates ranging from 71% to 98%, while stones with size more than 5 mm had expulsion rates ranging from 25% to 53%(6).

Many factors affect stone removal and must be considered while selecting MET for stones like ureteric spasm, location, size, and number of stones and duration for which it is present and also the ureteric architecture etc(7).

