Similar results were seen in another study showing that, individuals receiving just tamsulosin treatment needed a greater average analgesic dosage of 391.43 \pm 165.60 mg with a p-value of 0.005, which denotes substantial significance, the necessary(50).

Similarly, a study showed statistically significant difference in the amount of analgesics needed by patients treated with Silodosin compared to those treated with tamsulosin only. The robustness of the conclusion was highlighted by the fact that the group receiving Silodosin treatment required considerably fewer analgesics than the groups receiving Tamsulosin, with a p-value of < 0.001(51).

Conclusion

An effective treatment for ureteral stones is medical expulsive therapy. According to our findings, silodosin has a safer profile and is more successful than tamsulosin at ejecting ureteric stones.

Silodosin had an increased rate of stone expulsion and took less time in stone expulsion compared to those treated with Tamsulosin.

In addition, patients treated with silodosin reported fewer side effects, such as a retrograde ejaculation, orthostatic hypotension and headaches as compared to those taking Tamsulosin.

In addition, those who received Silodosin needed less analgesic medication than those who received Tamsulosin.

•

REFERENCES

- Ahmed AFAM, Al-Sayed AYS. Tamsulosin versus Alfuzosin in the Treatment of Patients with Distal Ureteral Stones: Prospective, Randomized, Comparative Study. Korean J Urol. 2010 Mar;51(3):193–7.
- 5. Pietropaolo A, Proietti S, Geraghty R, Skolarikos A, Papatsoris A, Liatsikos E, et al. Trends of 'urolithiasis: interventions, simulation, and

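### The stones behind the 19-point planning difference are not identified, 56% of analysed stones were not distal, and neither allocation nor analysis takes account of location

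*Combined protocol and SAP*

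**What the plan says.** The Inclusion Criteria ask for a "Solitary unilateral ureteral stone" under 10 mm on CT. No part of the ureter is excluded and there is no lower size limit.

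The Sample Size section assumes "an anticipated expulsion rate ranging from 58-64 percent in tamsulosin group and 78-83 percent in silodosin group with a risk difference of 19". The targets are 80% power at the 5% level, with 104 patients per arm after a 10% allowance for loss to follow-up. It gives no source, stone location or stone size for these rates.

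Elsewhere, the Literature Review reports that treating "distal ureteral stones with size less than 10 mm with tamsulosin and silodosin has resulted in a high output rates of 57-64" per cent on tamsulosin, against 80–84% on silodosin. The Discussion describes a trial of 4–10 mm distal stones with 61.2% v 80.3%.

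The Introduction lists location and size among the factors that affect stone removal, and the Data Collection section records both. Sample Selection describes only random allotment to two groups. The Data Analysis Procedure names one two-group t-test and no covariate.

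The null hypothesis says "silodosin can be used with the same efficacy for the treatment of lower urinary tract calculi". The Conclusion calls silodosin "more successful than tamsulosin at ejecting ureteric stones", with no limit on location.

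**The concern.** Two separate things are at stake.

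**Power.** A sample size is only as good as the match between the planning difference and the patients who can enter. If the 19 points were observed in distal stones and the true difference is smaller higher up, the average difference in the eligible population is below 19 and the power is below 80%. A reader cannot judge this, because the source population is not given.

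**Comparability.** The plan treats location as prognostic and measures it before randomisation, but neither balances it nor adjusts for it. If the arms end up with different location mixes, a crude comparison of removal times mixes the effect of the drug with the effect of where the stone lay.

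**Working it through.** **1. The plan's own figure.** The document does not say which pair within the two ranges was used. Take 64% v 83% (difference 0.19), two-sided 5%, 80% power, mean rate 0.735:

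- n = [1.96·√(2·0.735·0.265) + 0.8416·√(0.64·0.36 + 0.83·0.17)]² / 0.19² = (1.2233 + 0.5130)² / 0.0361 = 83.5
- with continuity correction: (83.5/4)·[1 + √(1 + 4/(83.5·0.19))]² = 93.7, so 94
- 94 × 1.10 = 103.4, so 104 per arm

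The stated 104 reproduces. The arithmetic is sound; the question is which population the inputs describe.

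**2. Closely similar pairs of rates in the document**

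| Place | Tamsulosin | Silodosin | Stones |
|---|---|---|---|
| Sample Size | 58–64% | 78–83% | not stated |
| Literature Review, randomised studies | 57–64% | 80–84% | distal, <10 mm |
| Discussion, single trial | 61.2% | 80.3% | distal, 4–10 mm |
| Discussion, another adult study | 61.5% | 82.4% | not stated |

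Each pair with a stated location is distal. The document gives no tamsulosin v silodosin rates for proximal or mid-ureter stones.

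**3. Location of the analysed stones** (characteristics table in Results)

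| | Tamsulosin | Silodosin | Total |
|---|---|---|---|
| Proximal | 28 | 26 | 54 |
| Mid | 8 | 38 | 46 |
| Distal | 41 | 38 | 79 |
| Total | 77 | 102 | 179 |

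Distal share: 79/179 = 44.1%. Non-distal share: 100/179 = 55.9%.

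**4. Power if the non-distal gain differs.** Assumptions: 61% on tamsulosin at every location, 19 points in distal stones, the analysed location mix, and 94 evaluable per arm (104 × 0.9 = 93.6).

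- Average difference: D = 0.441·19 + 0.559·g, where g is the non-distal gain in points.
- Power = Φ[(D − 1.96·SE₀)/SE₁], with SE₀ from the pooled rate and SE₁ from the separate rates.
- Example, g = 5: D = 8.4 + 2.8 = 11.2 points; rates 0.610 and 0.722; SE₀ = 0.0688; SE₁ = 0.0683; (0.1118 − 0.1348)/0.0683 = −0.34; power 37%.

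| Non-distal gain g (points) | Average D (points) | Power, 94 per arm | Power, 104 per arm |
|---|---|---|---|
| 0 | 8.4 | 22% | 24% |
| 5 | 11.2 | 37% | 40% |
| 9.5 | 13.7 | 52% | 56% |
| 15 | 16.8 | 71% | 75% |
| 19 | 19.0 | 82% | 86% |

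With 64% on tamsulosin, power at 94 per arm runs from 23% (g = 0) to 84% (g = 19).

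**5. Balance of location between arms.** Expected counts in the table above are 23.2/30.8 (proximal), 19.8/26.2 (mid) and 34.0/45.0 (distal). Chi-square = 16.6 on 2 df, p = 0.00025. Mid-ureter share: 8/77 = 10.4% on tamsulosin, 38/102 = 37.3% on silodosin. Most of the imbalance lies between mid and proximal: among non-distal stones the mid share is 8/36 = 22% v 38/64 = 59%.

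**6. Which outcome can be compared by location.** The removal-time rows sum to 6 + 14 + 57 = 77 and 52 + 37 + 13 = 102, so every analysed patient has a removal time within 28 days. Clearance at 4 weeks would be 100% in every location on that table; only time to removal can differ.

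**The case against.** **The source is inferred.** A reader might infer that the 19 points are known to come from distal 4–10 mm stones. The document does not say so. The Literature Review ranges are close to the planning ranges but not identical, and one close pair has no stated location. This objection stands, which is why the request is to state the source rather than to declare it distal.

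**A size mismatch.** The Introduction says "Stones smaller than 5 mm have passage rates ranging from 71% to 98" per cent, so a reader might infer that small stones dilute the planned difference. The nearest distal rates carry the same under-10 mm limit as eligibility, so small stones may already be in them. The 4–10 mm range rests on one trial, and the document gives no size distribution. No size dilution is claimed here.

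**An effect may exist outside the distal ureter.** The Literature Review cites meta-analyses favouring silodosin for ureteral stones in general, and enrolling all stones under 10 mm follows the guideline limit that the document cites. This is fair. If the gain is 19 points everywhere, no power is lost.

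**The result is positive.** A reader might infer that the pooled result rests on the planning figures and falls with them. It does not: a planning mismatch affects prospective power, and dilution pulls towards no difference, so it cannot explain a claimed benefit. Confounding by location is a different matter, and dilution gives no answer to it.

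**Conclusion.** The concern holds in two limited parts. First, the 80% power is conditional on a 19-point difference in all eligible stones, and the document neither gives the source of that figure nor supports it for the 56% of analysed stones that were not distal. The loss could be nil or large (82% down to 22% at 94 per arm). Where it falls depends wholly on an assumed non-distal gain, an assumed 61% tamsulosin rate and the analysed location mix.

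Second, and independent of those assumptions, the arms differ in location on the document's own counts (10% v 37% mid-ureter, p = 0.00025). The comparison is unadjusted, no outcome is shown by location, and stone size is not tabulated. The direction of any bias cannot be told, because removal times by location are not given. This opens the claimed difference to confounding; it does not show that the difference is wrong.

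**What to change.** 1. **Protocol.** Stratify allocation by stone location (distal v proximal/mid), with CT size as an optional second factor. Both are known before randomisation. This helps only further enrolment or a repeat of the trial; it cannot repair the present allocation.
2. **Data in hand.** Replace the unadjusted comparison with one of time to removal stratified by or adjusted for location and CT size, for example a stratified log-rank test. Use all three location levels where numbers allow, since the imbalance is mainly between mid and proximal. Report removal time by arm within distal and within proximal/mid stones, and tabulate stone size by arm.
3. **Sample Size section.** State the source population of the rates and of the 19 points, give the grounds for expecting the same difference in proximal and mid-ureter stones, and say that the 80% power is conditional on it.
4. **Wording.** Align the population in the null hypothesis with the eligible one, and word the Conclusion according to the location-adjusted result.

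The cost is low: recorded data, one or two extra tables and some rewording, with no extra patients or procedures. The downside is a less favourable power statement and small strata. Only 8 tamsulosin patients had mid-ureter stones, and the distal stones alone (41 v 38) give about 45–48% power for 19 points (61% v 80% to 64% v 83%), so the within-location results should be read as descriptive.
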